### **10.4.3**

#### **Analysis of the Secondary Endpoint(s)**

1. Freedom from ACR will be compared using Kaplan-Meier survival analysis and the log-rank test.
2. Composite rejection standardized score at 1 year follow-up will be presented as median (IQR) and will be compared using the Mann-Whitney U test
3. Treated episodes of rejection will be presented as frequencies and compared using chi-square test
4. Incidence of CLAD at 1 year will be presented as odds ratio with 95% confidence intervals and compared between groups using logistic regression.
5. Incidence of *de novo* DSA at 1 year will be presented as odds ratio with 95% confidence intervals and compared using between groups using logistic regression.
6. Mortality a 1 year post-transplant will be compared using Kaplan-Meier survival curves and log-rank analysis.

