## Protocol Summary

Title	Pilot Study Comparing early conversion to Extended-release Tacrolimus (ENVARSUS XR) to immediate-release Tacrolimus in lung transplant recipients
Short Title	Envarsus XR in Lung Transplant
Brief Summary	Patients undergoing a lung transplant will be enrolled. All patients will undergo lung transplantation with standard post-operative management, including triple immunosuppression. As soon as the patient is deemed appropriate to take medications via the oral route, they will be converted from IR tacrolimus to Envarsus XR. Patients will be followed per site's standard of care.
Phase	Pilot study
Objectives	To determine the feasibility of early conversion to Envarsus XR in patients who receive a lung transplant. To compare the impact of tacrolimus formulation on CKD, ACR, AMR, and de novo DSA within the first year post-lung transplant.
Methodology	Single-center, open-label study
Endpoint	Incidence of CKD, ACR, AMR, and de novo DSA in the first year post-lung transplant
Study Duration	Two years
Participant Duration	One year
Duration of IP administration	One year
Population	Adult patients undergoing lung transplantation
Study Sites	NYU Langone Hospital
Number of participants	Sixty patients (20 patients who received IR tacrolimus and 40 patients who will receive Envarsus XR)
Description of Study Agent/Procedure	Lung transplantation will be performed per standard-of-care techniques. All post-transplant management, including initial triple immunosuppression, will be carried out per standard of care. Once the patient is able to take medications via the oral route, they will be converted to Envarsus XR, which will be maintained for the first year post-lung transplant.
Reference Therapy	IR tacrolimus
Key Procedures	Patients in the Prospective Cohort will receive lung transplantation and post-operative management per standard protocol, including frequency of laboratory assays, surveillance bronchoscopy, and DSA assessment by single-antigen bead assay.
Statistical Analysis	Categorical variables will be compared using chi-square test or Fisher's exact test, as appropriate. Continuous variables will be compared using the Mann-Whitney U test for nonparametric data.

CONFIDENTIAL

This material is the property of the NYU School of Medicine and Langone Medical Center. Do not disclose or use except as authorized in writing by the study sponsor

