## **10.4 Description of Statistical Methods**

### **10.4.1**

#### **General Approach**

The study is a two-arm, non-randomized study comparing a prospective arm of patients receiving Envarsus XR to a historical control who received IR tacrolimus. Descriptive statistics will be used for baseline characteristics and to compare nominal outcomes such as de novo DSA and the incidence of CLAD at 1 year post-transplant. These data will be presented as frequencies and will be compared using Chi-square tests or Fishers exact test, as appropriate. The primary outcome freedom from ACR will be compared using Kaplan-Meier survival analysis and analyzed with the log-rank test. Continuous data will be presented as median (interquartile range) and compared using Mann-Whitney U test. A two-tailed P value of < 0.05 will be considered as significant for inferential tests.

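### CLAD and de novo DSA at 1 year are given two different analyses with no rule on which prevails, and the logistic regression has no provision for an arm with no events

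*Combined protocol and SAP*

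**What the plan says.** Section 10.4.3 lists an analysis for each secondary endpoint. Item 4 reads "Incidence of CLAD at 1 year will be presented as odds ratio with 95% confidence intervals and compared between groups using logistic regression". Item 5 treats de novo DSA alike: "DSA at 1 year will be presented as odds ratio with 95% confidence intervals and compared using between groups using logistic regression". Neither item names covariates, a fitting method, a type of interval or a fallback for sparse counts.

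Section 10.4.1 uses descriptive statistics "to compare nominal outcomes such as de novo DSA and the incidence of CLAD at 1 year post-transplant", so it names the same two endpoints. It continues: "These data will be presented as frequencies and will be compared using Chi-square tests or Fishers exact test, as appropriate". The Protocol Summary agrees with 10.4.1: "Categorical variables will be compared using chi-square test or Fisher's exact test, as appropriate". Neither place says when chi-square gives way to Fisher.

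These comparisons are meant as inference. Section 10.4.1 adds "A two-tailed P value of < 0.05 will be considered as significant for inferential tests". The Protocol Summary sets the group sizes: "Sixty patients (20 patients who received IR tacrolimus and 40 patients who will receive Envarsus XR". Section 10.3 restricts efficacy analyses to patients who complete the first year, so fewer than 40 may be analysed in the Envarsus XR arm.

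**The concern.** There are two separate problems.

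The first is a contradiction in current text. Each endpoint has a logistic regression P value, a chi-square P value and a Fisher P value available, all judged against 0.05. The comparison is open-label and the historical controls have already completed their year, so control outcomes can be known before the analysis is settled. A plan that leaves the test open in that setting cannot show that the test was chosen independently of the result.

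The second concerns the odds ratio itself. For a two-group comparison, the maximum-likelihood odds ratio is the cross-product ratio of the 2×2 table. If one arm has no events, that ratio is zero or infinite and a Wald interval has no meaning. A group of 20 can be empty by chance when the outcome is uncommon, and the plan does not say what would then be reported.

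**Working it through.** **Inputs.** Group sizes 40 and 20 (Protocol Summary, study schematic, section 10.5). Two-sided 0.05 (section 10.4.1). Incidence of CLAD and of de novo DSA: not given anywhere, so a range is assumed. Completers: no dropout rate is given; 40 is used, with an assumed 32 as a variant. There is no power figure to reproduce, because section 10.5 declines to calculate one. The stated sizes are consistent: 40 + 20 = 60 and 40/20 = 2.

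**1. Can the choice of section change the conclusion?** Take 5/40 versus 7/20, with no empty cell.
- Logistic regression: OR = (5×13)/(35×7) = 65/245 = 0.27; log OR = −1.327; SE = √(1/5 + 1/35 + 1/7 + 1/13) = 0.670; z = −1.98; Wald P = 0.0475; 95% CI = exp(−1.327 ± 1.96×0.670) = 0.07 to 0.99.
- Fisher's exact test: P = 0.083. The smallest expected count is 12×20/60 = 4.0, so many analysts would use Fisher here.
- Uncorrected chi-square: P = 0.040.

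The result is significant under 10.4.3 and not significant under 10.4.1 with Fisher. The two tests offered by 10.4.1 also differ from each other.

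**2. How often does this happen?** All tables for 40 versus 20 were enumerated, taking 10.4.1 to mean Fisher if the smallest expected count is below 5 and uncorrected chi-square otherwise (an assumption). Of the 39×19 = 741 tables without a zero cell, the Wald test and the 10.4.1 test fall on opposite sides of 0.05 in 12. The probability of meeting such a table was 0% to 4.8% over the rates tried.

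**3. Chance that an arm has no events.** For rate p in both arms: 1 − [1 − (1−p)^40]×[1 − (1−p)^20].

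| Assumed rate | No events in 40 | No events in 20 | Either arm |
|---|---|---|---|
| 3% | 0.296 | 0.544 | 68% |
| 5% | 0.129 | 0.358 | 44% |
| 10% | 0.015 | 0.122 | 13.5% |
| 15% | 0.002 | 0.039 | 4.0% |
| 20% | 0.000 | 0.012 | 1.2% |

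With 5% on Envarsus XR and 10% in controls: 1 − (1 − 0.129)(1 − 0.122) = 23%. With 32 completers and equal rates: 48% at 5% and 15% at 10%.

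**4. What an empty arm does.** For 0/40 versus 3/20 the ordinary fit diverges: two routines returned log ORs of −22 and −32, with standard errors of 12,564 and 3.5 million, and Wald P about 1.00. For the same data, Fisher gives P = 0.033, uncorrected chi-square 0.012 and the ordinary likelihood-ratio test 0.009.

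**5. Does the proposed method work on these tables?** For a 2×2 table, the Firth likelihood equals, up to a constant, the ordinary likelihood with 0.5 added to each cell.
- 0/40 versus 3/20: OR = (0.5/40.5)/(3.5/17.5) = 0.06. Maximised log-likelihood: 0.5 ln(0.5/41) + 40.5 ln(40.5/41) + 3.5 ln(3.5/21) + 17.5 ln(17.5/21) = −12.162. Under no effect: 4 ln(4/62) + 58 ln(58/62) = −14.831. Statistic 2×2.669 = 5.34 on 1 df; P = 0.021. The odds ratios at which the statistic equals 3.84 give a 95% CI of 0.0004 to 0.69.
- 5/40 versus 7/20: OR = (5.5/35.5)/(7.5/13.5) = 0.28. Statistic 2×(31.839 − 29.849) = 3.98; P = 0.046; 95% CI 0.07 to 0.98.

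The estimate is finite in both cases. Interval and P value agree by construction, because both come from the same likelihood.

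**The case against.** The strongest reply is that the sections can be read together: 10.4.1 is a general approach, 10.4.3 is specific to each endpoint, and Fisher's exact test, which is valid in small samples, is already planned. This has some force, and one sentence on precedence would settle the contradiction. But 10.4.1 is not generic here, since it names CLAD and de novo DSA. Giving precedence to 10.4.3 would still leave the empty-arm case without a rule.

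A reader might infer that events will be few and that the odds ratio will probably fail. The documents do not support that. They state no incidence, and the two outcomes need not share one. With equal rates, failure is more likely than not only below an incidence of about 4.4%, and it is close to negligible at 20%. It may concern one endpoint, both or neither.

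Nor do the documents say that the model is unpenalised or that the interval is Wald. The text says only logistic regression; the standard fit is an inference. What stands is that no alternative is named.

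It is also true that the competing tests usually agree, and that these are secondary endpoints of an unpowered pilot whose primary endpoint is descriptive. That limits the consequences but does not remove the inconsistency.

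Replacing the odds ratio with a risk difference would be a preference rather than a correction. Fisher's P with a separately chosen interval can also conflict. For 5/40 versus 7/20, the Newcombe interval for the risk difference (−0.453 to −0.008) excludes zero while Fisher's P is 0.083. For 0/40 versus 3/20, the exact conditional interval for the odds ratio reaches 1.15 while Fisher's P is 0.033.

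**Conclusion.** The contradiction is certain from the text: two endpoints, two planned analyses and no rule of precedence. It can decide significance, as 5/40 versus 7/20 shows, though in tables without an empty cell this is uncommon (at most 4.8% over the rates tried).

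The missing sparse-data rule is also certain. How much it matters depends on incidence, which the documents do not give. With equal rates and all 40 and 20 patients analysed, the chance of no finite odds ratio is 44% at 5%, 13.5% at 10%, 4% at 15% and about 1% at 20%. It is somewhat higher if completers are fewer or if Envarsus XR lowers the rate, as section 10.2 hypothesises. The supportable statement is that the planned estimate may not exist; that it is likely to fail is not established.

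The items need correcting as written, but nothing here affects the primary endpoint.

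**What to change.** In section 10.4.3, items 4 and 5, keep the odds ratio but state that it is estimated by Firth penalised logistic regression, with a profile penalised-likelihood 95% CI and the matching penalised likelihood-ratio P value, and that this is the single inferential result for each endpoint.

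In section 10.4.1, keep the presentation of frequencies for de novo DSA and CLAD but remove the chi-square/Fisher comparison for these two. Add the exception to the Protocol Summary.

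The cost is a change of wording and a little more analysis work. The estimate is pulled slightly toward no effect (0.27 becomes 0.28 for 5/40 versus 7/20). No patients, visits or data are added.

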### **10.4.4**

#### **Safety Analyses**

Safety endpoints include worsening chronic kidney disease and discontinuation of therapy will be analyzed as changes from baselines and summary data during the course of treatment, respectively. These will be compared as linear regression and frequencies using the chi-square test, respectively. All AEs will be ascertained and reported by the PI.

### **10.4.5**

#### **Adherence and Retention Analyses**

Adherence to the protocol will be assessed by the study team in direct conversation with subjects during routine visits, and will be assessed clinically by evaluation tacrolimus C0 levels. Failure to maintain significant tacrolimus C0 levels will prompt more detailed direct patient inquiries regarding medication adherence.

CONFIDENTIAL

This material is the property of the NYU School of Medicine and Langone Medical Center. Do not disclose or use except as authorized in writing by the study sponsor

#### **10.4.6**

#### **Baseline Descriptive Statistics**

Baseline statistics including but not limited to age, gender, etiology of lung disease, type of lung transplant, lung allocation score, details of the requirement for mechanical ventilation or extracorporeal membrane oxygenation, and ischemic time of the organ will be collected for each group. These data will be compared using chi-square tests to assess for baseline imbalances.

#### **10.4.7**

#### **Planned Interim Analysis**

No interim analysis is planned.

##### **10.4.7.1 Safety Review**

Any patient death will result in halting of any further enrollment in the study and an assessment of whether the death was related to Envarsus XR exposure or complications thereof. Even in the event of a patient death, currently enrolled patients who are actively being treated with Envarsus XR and tolerating therapy will continue to receive therapy so as not to put them at risk for rejection as a consequence of converting therapy. If the patient death is deemed related to Envarsus XR, enrolled patients receiving Envarsus XR will be switched to an alternative therapy including, but not limited to: IR tacrolimus, cyclosporine, sirolimus, everolimus, mycophenolate, belatacept, or some combination thereof.

##### **10.4.7.2 Efficacy Review**

There will be no interim analyses performed due to the small sample size and anticipated short duration of enrollment for the study.

#### **10.5 Sample Size**

We plan to prospectively enroll 40 patients into the Envarsus XR arm to provide a 2:1 sample size with a historical control of patients who received IR tacrolimus. The sample size of 40 patients for the Prospective Cohort was chosen based on the expected number of lung transplants performed in one year at NYULH. The Historical Control Cohort sample size includes all patients who were transplanted at NYULH and completed one year of follow-up post lung transplant while maintained on IR tacrolimus. The 2:1 sample size was chosen as the purpose of the study is to gain experience with Envarsus XR in lung transplant recipients and IR tacrolimus has many years of clinical use. As this is a pilot study, there will be no power calculations.

### **11 Source Documents and Access to Source Data/Documents**

Source data is all information, original records of clinical findings, observations, or other activities in a clinical trial necessary for the reconstruction and evaluation of the trial. Source data are contained in source documents. Examples of these original documents, and data records include: hospital records, clinical and office charts, laboratory notes, memoranda, subjects' diaries or evaluation checklists, pharmacy dispensing records, recorded data from automated instruments, copies or transcriptions certified after verification as being accurate and complete, microfiches, photographic negatives, microfilm or magnetic media, x-rays, subject files, and records kept at the pharmacy, at the laboratories, and at medico-technical departments involved in the clinical trial. It is acceptable to use CRFs as source documents. If this is the case, it should be stated in this section what data will be collected on CRFs and what data will be collected from other sources.

The study case report form (CRF) is the primary data collection instrument for the study. All data requested on the CRF must be recorded. All missing data must be explained. If a space on the CRF is left blank because the procedure was not done or the question was not asked, write "N/D". If the item is not applicable to the individual case, write "N/A". All entries will be stored in REDCap.

Access to study records will be limited to IRB-approved members of the study team. The investigator will permit study-related monitoring, audits, and inspections by the IRB/EC, the sponsor, government regulatory bodies, and University compliance and quality assurance groups of all study related

CONFIDENTIAL

This material is the property of the NYU School of Medicine and Langone Medical Center. Do not disclose or use except as authorized in writing by the study sponsor

documents (e.g. source documents, regulatory documents, data collection instruments, study data etc.). The investigator will ensure the capability for inspections of applicable study-related facilities (e.g. pharmacy, diagnostic laboratory, etc.).

Participation as an investigator in this study implies acceptance of potential inspection by government regulatory authorities and applicable University compliance and quality assurance offices.

## **12 Quality Assurance and Quality Control**

QC procedures will be implemented beginning with the data entry system and data QC checks that will be run on the database will be generated. Any missing data or data anomalies will be communicated to the site(s) for clarification/resolution.

Following written SOPs, the monitors will verify that the clinical trial is conducted and data are generated, documented (recorded), and reported in compliance with the protocol, GCP, and the applicable regulatory requirements (e.g., Good Laboratory Practices (GLP), Good Manufacturing Practices (GMP)).

The investigational site will provide direct access to all trial related sites, source data/documents, and reports for the purpose of monitoring and auditing by the sponsor, and inspection by local and regulatory authorities.

## **13 Ethics/Protection of Human Subjects**

### **13.1 Ethical Standard**

The investigator will ensure that this study is conducted in full conformity with Regulations for the Protection of Human Subjects of Research codified in 45 CFR Part 46, 21 CFR Part 50, 21 CFR Part 56, and/or the ICH E6.

### **13.2 Institutional Review Board**

The protocol, informed consent form(s), recruitment materials, and all participant materials will be submitted to the IRB for review and approval. Approval of both the protocol and the consent form must be obtained before any participant is enrolled. Any amendment to the protocol will require review and approval by the IRB before the changes are implemented to the study. All changes to the consent form will be IRB approved; a determination will be made regarding whether previously consented participants need to be re-consented.

### **13.3 Informed Consent Process**

#### **13.3.1 Consent/Accent and Other Informational Documents Provided to Participants (Envarsus XR Prospective Cohort)**

Consent forms describing in detail the study agent, study procedures, and risks are given to the participant and written documentation of informed consent is required prior to starting intervention/administering study product. The informed consent document to be used is submitted with this protocol.

#### **13.3.2 Consent Procedures and Documentation**

Informed consent is a process that is initiated prior to the individual's agreeing to participate in the study and continues throughout the individual's study participation. Extensive discussion of risks and possible benefits of participation will be provided to the participants and their families. Consent forms will be IRB-approved and the participant will be asked to read and review the document. The investigator will explain the research study to the participant and answer any questions that may arise. All participants will receive a verbal explanation in terms suited to their comprehension of the purposes, procedures, and potential risks of the study and of their rights as research participants. Participants will have the opportunity to carefully review the written consent form and ask questions prior to signing. The participants should have

CONFIDENTIAL

This material is the property of the NYU School of Medicine and Langone Medical Center. Do not disclose or use except as authorized in writing by the study sponsor

the opportunity to discuss the study with their surrogates or think about it prior to agreeing to participate. The participant will sign the informed consent document prior to any procedures being done specifically for the study. The participants may withdraw consent at any time throughout the course of the trial. A copy of the signed informed consent document will be given to the participants for their records. The rights and welfare of the participants will be protected by emphasizing to them that the quality of their medical care will not be adversely affected if they decline to participate in this study.

A copy of the signed informed consent document will be stored in the subject's research record. The consent process, including the name of the individual obtaining consent, will be thoroughly documented in the subject's research record. Any alteration to the standard consent process (e.g. use of a translator, consent document presented orally, etc.) and the justification for such alteration will likewise be documented.

### **13.4 Participant and Data Confidentiality**

Information about study subjects will be kept confidential and managed according to the requirements of the Health Insurance Portability and Accountability Act of 1996 (HIPAA). Those regulations require a signed subject authorization informing the subject of the following:

- What protected health information (PHI) will be collected from subjects in this study
- Who will have access to that information and why
- Who will use or disclose that information
- The rights of a research subject to revoke their authorization for use of their PHI.

In the event that a subject revokes authorization to collect or use PHI, the investigator, by regulation, retains the ability to use all information collected prior to the revocation of subject authorization. For subjects that have revoked authorization to collect or use PHI, attempts should be made to obtain permission to collect at least vital status (i.e. that the subject is alive) at the end of their scheduled study period.

Participant confidentiality is strictly held in trust by the participating investigators, their staff, and the sponsor(s) and their agents. Therefore, the study protocol, documentation, data, and all other information generated will be held in strict confidence. No information concerning the study or the data will be released to any unauthorized third party without prior written approval of the sponsor.

The study monitor, other authorized representatives of the sponsor, representatives of the IRB or pharmaceutical company supplying study product may inspect all documents and records required to be maintained by the investigator, including but not limited to, medical records (office, clinic, or hospital) and pharmacy records for the participants in this study. The clinical study site will permit access to such records.

The study participant's contact information will be securely stored at the site for internal use during the study. At the end of the study, all records will continue to be kept in a secure location for as long a period as dictated by local IRB and Institutional regulations.

Study participant research data, which is for purposes of statistical analysis and scientific reporting, will be transmitted to and stored at NYU Langone Medical Center. This will not include the participant's contact or identifying information. Rather, individual participants and their research data will be identified by a unique study identification number. The study data entry and study management systems used by the site and by NYU Langone Medical Center research staff will be secured and password protected. At the end of the study, all study databases will be de-identified and archived at the NYU Langone Medical Center.

CONFIDENTIAL

This material is the property of the NYU School of Medicine and Langone Medical Center. Do not disclose or use except as authorized in writing by the study sponsor

